7.1.2 Description of Type of Study

This is a multi-center, randomized, double-blind, placebo-controlled Phase III clinical trial that will include at least 56 subjects with SCD who are hospitalized for ACS. Individuals who meet entry criteria will be randomized to receive either dexamethasone or placebo. Dexamethasone will be administered initially as 0.3 mg/kg by mouth every 12 hours for a maximum of 4 doses (2 days) or until discharge from the hospital, whichever occurs first. Afterward, the study drug will be tapered over 6 days for a total duration of therapy not to exceed 8 days. Due to possible age-related and ACS severity-related differences in the duration of signs and symptoms of ACS, randomization will be stratified by age and severity of ACS (see Section 8.3). We are enrolling a maximum of 112 pediatric subjects. We will enroll adult subjects at the rate site participation will allow, which we anticipate will be no more than 56 subjects. Interim analyses will be performed when a total of 56 subjects and 112 subjects have completed their hospital stay. If we do not stop enrollment after these interim analyses are completed, we will continue to enroll up to a maximum total of 112 pediatric subjects. The efficacy and safety of dexamethasone will be compared to placebo in the context of standard supportive care for ACS.

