13.2.4 Interim Analyses

Two formal interim analyses will be performed on the primary efficacy variable. The first interim analysis will take place when 56 subjects have resolved signs and symptoms of ACS *or* have been discharged from the hospital. To test for differences between the treatment arms, the same F-test from the GLMM specified in the primary analysis will be used with a Peto stopping boundary of $p < 0.001$.⁷⁸ The study will be stopped if significant efficacy is identified. The second interim analysis will be performed when 112 subjects have resolved signs and symptoms of ACS *or* have been discharged from the hospital. The primary efficacy hypothesis will be tested at the $\alpha = 0.01$ level on the total subjects,

and the 0.05 level for the children. If significant efficacy will be identified for total subjects and for children, the study will be stopped. Otherwise, the study will continue enrollment to 112 children, after which the primary efficacy hypothesis will be tested on the $\alpha = 0.039$ level. By utilizing these alpha levels for each test and a step-down procedure for the pediatric sub-population, the overall study alpha level for the test of the primary hypothesis remains at the 0.05 level.

In order to ensure that future subjects are not exposed to study drug unnecessarily, the DSMB will also be provided with the conditional probability of completing a successful trial at the interim analyses under three scenarios: (1) the treatment difference continues to be the same as in the first portion of the trial; (2) the treatment difference is zero for the next portion of the trial; (3) the treatment difference is 30 hours for the next portion of the trial. Based on this information, the DSMB can make an informed decision about the futility of the trial.

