Based on these preliminary findings, we anticipate that dexamethasone will decrease the LOS by 30 hours (compared to 33 hours for Bernini and 27 hours for Huh) and we will therefore power our tests to detect a 30-hour difference. The data from Huh et al (2004)⁴⁸ gives evidence that the LOS for ACS may have a lognormal distribution, but the clinical hypothesis makes a statement about differences in mean of LOS not the natural log of LOS. Assuming the LOS in each treatment group is distributed as lognormal, normal distribution based statistical analysis methodologies can be used for analysis of the natural log of LOS. With the lognormal assumption, the mean LOS for each treatment group is a function of both the mean and variance of the natural log of LOS, so the following sample size calculations had to consider possible lognormal distributions and the mean difference on the untransformed scale.

Table 13.2 presents the lognormal transformed results of Table 13.1, which we used in the sample size calculations.

Table 13.2 Effect of dexamethasone on natural log of the duration of hospitalization for ACS in children

	Bernini et al, (1998) Ln(Duration of hospitalization)	Huh et al (2004) Ln(Duration of hospitalization)
Placebo	4.217 (SD=0.574)	4.216 (SD=0.707)
Dexamethasone	3.795 (SD=0.331)	3.954 (SD=0.560)

The hypothesis tested is: shortened duration of ACS signs and symptoms/hospitalization by at least 30 hours for children with SCD who are hospitalized for the treatment of ACS and receive dexamethasone. Using LOS as a surrogate, we used a two group Satterthwaite t-test of equal means (unequal variances, equal n's) to test the difference in natural log of the hospitalization duration between treatment groups. We additionally

assumed a two-sided alpha of 0.05 and 90% power. Several scenarios were explored in which we varied the lognormal variance parameter and lognormal mean parameter for the two treatment groups according to the ranges found in the two pilot studies.

If we assume that

- we are testing a two-sided hypothesis,
- the treatment effects seen in children are the same in adults,
- the lognormal population standard deviation for the placebo group is 0.6,
- the lognormal population standard deviation of the dexamethasone group is 0.3,
- the lognormal mean of the placebo group is 4.25,
- the lognormal mean of the dexamethasone group 3.95, (corresponding to a mean difference in LOS between the two treatment groups of 30 hours),

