- the Type I error rate is 0.05,
- and the power is 90%,

then the necessary amount of subjects needed per treatment group is 54. We do not anticipate many dropouts prior to the assessment of the primary endpoint because the population should remain in the hospital under observation until that time. However, we will add two more subjects to each treatment arm to compensate for potential withdrawals, so the total number of subjects needed per treatment group is 56.

We have also explored alternative scenarios and concluded that 56 subjects per treatment group is sufficient under the following conditions:

- the lognormal population standard deviation for the placebo group ≤ 0.6 (and thus follows the Bernini⁴⁷ study), and
- the lognormal population standard deviation of the dexamethasone group ≤ 0.5 (and thus is in the range of both the Bernini and Huh study), and
- the lognormal mean of the placebo group is 4.0, 4.1, 4.2, or 4.3, and

- the lognormal mean of the dexamethasone group is 3.6, 3.7, 3.8, 3.9, or 4.0, and
- the mean difference in LOS between the two treatment groups is ≥ 30 hours.

If we wish to vary assumptions, we would see differences in the number of subjects needed.

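### Section 13.4 sizes the trial at two-sided 0.05, but the deciding test is at 0.039, so the stated 90% power at 54 per arm is not the power of that test

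*Protocol*

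**What the plan says.** **Testing levels.** Protocol section 13.2.4 and the synopsis set three tests of the primary hypothesis:

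- 0.001 at 56 subjects;
- 0.01 on all subjects at 112 subjects, with stopping also requiring significance in children (at 0.05 in 13.2.4);
- 0.039 once 112 children are enrolled.

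Section 13.2.4 adds that, with these levels and a step-down for children, "the overall study alpha level for the test of the primary hypothesis remains at the 0.05 level". It does not say whether the 0.039 test is run on all subjects or on children.

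**Sizing.** Section 13.4 "assumed a two-sided alpha of 0.05 and 90% power". It lists "the Type I error rate is 0.05", "the lognormal population standard deviation for the placebo group is 0.6" and "the lognormal population standard deviation of the dexamethasone group is 0.3", with log means of 4.25 and 3.95 and a Satterthwaite t-test with equal group sizes. It concludes: "then the necessary amount of subjects needed per treatment group is 54". Two more per arm are added for withdrawals, making 56. The interim looks and the 0.039 level are not mentioned there.

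**Final size.** Section 7.1.2 caps children at 112 and says of adults: "We will enroll adult subjects at the rate site participation will allow, which we anticipate will be no more than 56 subjects". No minimum number of adults is set.

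**The concern.** A sample size calculation should describe the test that decides the trial. Here it describes a test at 0.05, while the total population is tested only at 0.001, 0.01 and 0.039. The one test at 0.05 is the added condition on children at the second look, which cannot bring success by itself.

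A stricter level lowers power at a given size, so the stated 90% at 54 per arm cannot hold for the 0.039 test. It holds still less at the 112-subject look, where the planned 56 per arm are tested at 0.01. Readers of 13.4, including the monitoring board when it judges futility from conditional probabilities of success, would take the design to be a little stronger than it is.

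**Working it through.** **Inputs (all from 13.4).** Log-scale difference 4.25 − 3.95 = 0.30; SDs 0.6 (placebo) and 0.3 (dexamethasone); equal arms; two-sided Satterthwaite t-test. As a check on the inputs, the implied means are exp(4.25 + 0.6²/2) = 83.9 h and exp(3.95 + 0.3²/2) = 54.3 h. The difference is 29.6 h, in line with the stated 30 h.

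**Formulas.**
- Standard error: SE = √((0.36 + 0.09)/n)
- Noncentrality: 0.30/SE
- Degrees of freedom: (n − 1)(0.36 + 0.09)²/(0.36² + 0.09²) = 1.4706(n − 1)
- Power: the probability that a noncentral t with these parameters exceeds the two-sided critical value in absolute size

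**The plan's own figure.** With n = 54, SE = 0.0913, noncentrality = 3.286 and df = 77.9. At 0.05 the critical value is 1.991 and power is 90.1%. With n = 53, power is 89.5%. The stated 54 is therefore reproduced, at two-sided 0.05.

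**The same calculation at the levels actually used.**

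| n per arm | Noncentrality | Power at 0.05 | Power at 0.039 | Power at 0.01 |
|---|---|---|---|---|
| 54 | 3.286 | 90.1% | 88.0% | 73.9% |
| 56 | 3.347 | 91.1% | 89.2% | 75.9% |
| 57 | 3.376 | 91.6% | 89.8% | 76.8% |
| 58 | 3.406 | 92.0% | 90.3% | 77.7% |
| 84 | 4.099 | 98.2% | 97.7% | 92.9% |

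At 0.039, 58 per arm is the smallest size that reaches 90%. The row for 84 per arm is 112 children plus 56 adults (168/2), under 13.4's assumption that adults share the children's effect. The 0.01 column does not count the added children's condition, which can only lower the chance of stopping at the second look.

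The earlier looks do not make up the gap when the final analysis is 112 subjects, because a result that crosses 0.01 at 112 subjects also crosses 0.039 there. In a normal approximation at 56 per arm, the single test at 0.039 has 90.02% power and the three-look sequence 90.04%.

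**Overall error.** 0.001 + 0.01 + 0.039 = 0.050. The probability of at least one false positive cannot exceed this sum, whatever the correlation between the looks. The actual error, from normal statistics with correlation √(N_i/N_j) between looks at 56, 112 and N subjects, is:

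| Final N | Overall two-sided error |
|---|---|
| 120 | 0.039 |
| 140 | 0.041 |
| 168 | 0.043 |

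Adding the children's condition at the second look gives, with 56 adults, 0.042 for a final test on all subjects and 0.043 for one on children only. With 10 adults the figures are 0.039 and 0.040.

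**Level that would use the full 0.05.** Under the written second-look rule, keeping 0.001 and 0.01, the final level solves to about 0.050 with no adults. With 56 adults it is about 0.048 (all subjects) or 0.047 (children only). The range is about 0.046-0.050, allowing for simulation error.

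**The case against.** **The shortfall is slight.** The plan is 56 per arm, not 54, and 89.2% is under one point below 90%. The normal approximation gives 56 per arm at 0.039. This is fair as to size. But 13.4 sizes with the Satterthwaite t, and the two extra per arm are meant for withdrawals, so 88.0% to 89.2% is the honest range.

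**Adults will close the gap.** Section 13.1 puts all analyses on the intent-to-treat population, which points to a pooled final test. Four adults would then bring it to 116/2 = 58 per arm. This stands if the final test is pooled and adults respond as children do. However, 13.2.4 does not name the population, 13.4 words its hypothesis for children, and no minimum number of adults is set.

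**Uncertainty in the SDs matters more.** It does. With the second pilot study's log SDs in Table 13.2 (0.707 and 0.560) and a difference of 0.30, 56 per arm gives about 69% at 0.05 and 66% at 0.039. That is no reason to report power at a level that is not used.

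**Stronger readings that the protocol does not support.**

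- A reader might infer that the claim of an overall 0.05 is false, since 0.039 looks like 0.05 with the earlier levels subtracted (an inference; the derivation is not stated). Such a split is valid under any dependence between looks. The claim is true as a ceiling, and a final p of 0.045 called negative contradicts nothing in 13.2.4.
- A reader might infer inflation from the unnamed final population. If success in either all subjects or children counted, simulated error with 56 adults would be about 0.064. But the protocol speaks of a step-down and states no either-or rule.

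**Conclusion.** The point holds as a mismatch between 13.4 and 13.2.4. The 54 per arm for 90% power belongs to a 0.05 test that is never run on the total population. At the deciding level of 0.039, power is 88.0% with 54 and 89.2% with 56 per arm, 58 per arm are needed for 90%, and the second look has about 74-76%.

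These figures rest on 13.4's own planning values. The 88-89% applies to a final test on 112 subjects, such as 112 children alone. With 56 adults pooled and the same effect, power at 0.039 is 97.7%.

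Type I error is controlled: at most 0.05, and about 0.039-0.043 for a single final test. The defect is a small misstatement of power. It does not undermine the trial's error control.

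**What to change.** **Section 13.4.** Replace the alpha of 0.05 by the final level of 0.039. State power of 88-89% for 112 children (54 to 56 per arm), with 58 per arm needed for 90%. Give about 74-76% for the 112-subject look at 0.01. If the final test uses all subjects, add the pooled power, for example 97.7% at 84 per arm, with its assumption of a common effect.

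**Section 13.2.4.** Describe 0.05 as an upper bound on the overall error, and name the population of the 0.039 test so that the right power figure can be attached.

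**Optional.** Once that population is fixed, the final level could be solved from the joint distribution of the three looks at the enrolled numbers of children and adults (about 0.046-0.050 under the written rule). This is a modest efficiency gain and not a correction. It gives up a single level fixed in advance, and it should not be adopted while the final population is open.

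**Cost.** A few sentences in 13.4 and 13.2.4. No extra subjects and no change to the conduct of the trial.

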13.3 Statistical Considerations

13.3.1 Covariates

Age group and severity group will be used as covariates in the primary analysis. Baseline laboratory measurements will be controlled for when analyzing laboratory outcomes. Center will be included in the models as permitted by sample size. Other covariates may be considered in the analysis of clinical, laboratory, and safety outcomes as needed.

13.3.2 Multi-center Studies

Randomization will be stratified by severity group, center and age group to preserve a balance across treatment groups. Center effects will be examined as permitted by sample size.

13.3.3 Multiple Comparisons and Multiplicity

One primary hypothesis will be tested and other reported p-values will be considered descriptive. Hence, no multiple comparisons adjustments will be made.

13.3.4 Examination of Subgroups

Analyses may be stratified by severity of ACS strata (see Section 8.3). If warranted, exploratory analyses may examine the treatment effect in severity of ACS subgroups.

13.3.5 Missing Data

Data from subjects who are lost to follow-up will be used as much as possible since the analyses allow for missing data. The validity of the primary analysis will depend on the assumed distribution and minimal censoring. If a higher number of deaths or withdrawals prior to discharge occur than expected, the secondary survival analysis will provide an important sensitivity analysis. All longitudinal analyses (e.g., pain scores and laboratory measurements) will utilize models that do not require eliminating the subject for intermittent missing data.

13.4 Sample Size

At least 56 subjects will be enrolled into this trial. Subjects will be randomized to one of two treatment groups: placebo or dexamethasone.

The measurement of primary interest is the duration of ACS signs and symptoms/hospitalization. Previous studies using dexamethasone to treat ACS reported hospital length of stay (LOS) instead of duration of symptoms. Since subjects are generally not discharged until their symptoms are resolved and are discharged relatively quickly after the resolution of symptoms, the LOS is also a surrogate endpoint for the purposes of calculating an appropriate sample size for the duration of symptoms. It is anticipated that LOS will be more variable than duration of symptoms due to the impact of administrative considerations (e.g. subjects not being discharged in the middle of the night). Therefore, we expect that any sample size calculations based on LOS data will be conservative for the endpoint of symptom duration, helping ensure that the study will examine enough subjects to test the primary hypothesis.

The raw data from the follow-up study by Huh et al (2004), as described in Section 5, and the published statistics from the Bernini et al (1998) study were available to use for

sample size calculations. The average LOS for ACS in children together with the standard deviation as observed in the two pilot studies are presented in Table 13.1.

Table 13.1 Effect of dexamethasone on duration of hospitalization for ACS in children

	Bernini et al, (1998) Duration of hospitalization (hrs)	Huh et al (2004) Duration of hospitalization (hrs)
Placebo	80 (SD=50)	87 (SD=70)
Dexamethasone	47 (SD=16)	60 (SD=37)

Based on these preliminary findings, we anticipate that dexamethasone will decrease the LOS by 30 hours (compared to 33 hours for Bernini and 27 hours for Huh) and we will therefore power our tests to detect a 30-hour difference. The data from Huh et al (2004)⁴⁸ gives evidence that the LOS for ACS may have a lognormal distribution, but the clinical hypothesis makes a statement about differences in mean of LOS not the natural log of LOS. Assuming the LOS in each treatment group is distributed as lognormal, normal distribution based statistical analysis methodologies can be used for analysis of the natural log of LOS. With the lognormal assumption, the mean LOS for each treatment group is a function of both the mean and variance of the natural log of LOS, so the following sample size calculations had to consider possible lognormal distributions and the mean difference on the untransformed scale.

Table 13.2 presents the lognormal transformed results of Table 13.1, which we used in the sample size calculations.

Table 13.2 Effect of dexamethasone on natural log of the duration of hospitalization for ACS in children

	Bernini et al, (1998) Ln(Duration of hospitalization)	Huh et al (2004) Ln(Duration of hospitalization)
Placebo	4.217 (SD=0.574)	4.216 (SD=0.707)
Dexamethasone	3.795 (SD=0.331)	3.954 (SD=0.560)

The hypothesis tested is: shortened duration of ACS signs and symptoms/hospitalization by at least 30 hours for children with SCD who are hospitalized for the treatment of ACS and receive dexamethasone. Using LOS as a surrogate, we used a two group Satterthwaite t-test of equal means (unequal variances, equal n's) to test the difference in natural log of the hospitalization duration between treatment groups. We additionally

assumed a two-sided alpha of 0.05 and 90% power. Several scenarios were explored in which we varied the lognormal variance parameter and lognormal mean parameter for the two treatment groups according to the ranges found in the two pilot studies.

If we assume that

- we are testing a two-sided hypothesis,
- the treatment effects seen in children are the same in adults,
- the lognormal population standard deviation for the placebo group is 0.6,
- the lognormal population standard deviation of the dexamethasone group is 0.3,
- the lognormal mean of the placebo group is 4.25,
- the lognormal mean of the dexamethasone group 3.95, (corresponding to a mean difference in LOS between the two treatment groups of 30 hours),
- the Type I error rate is 0.05,
- and the power is 90%,

then the necessary amount of subjects needed per treatment group is 54. We do not anticipate many dropouts prior to the assessment of the primary endpoint because the population should remain in the hospital under observation until that time. However, we will add two more subjects to each treatment arm to compensate for potential withdrawals, so the total number of subjects needed per treatment group is 56.

We have also explored alternative scenarios and concluded that 56 subjects per treatment group is sufficient under the following conditions:

- the lognormal population standard deviation for the placebo group ≤ 0.6 (and thus follows the Bernini⁴⁷ study), and
- the lognormal population standard deviation of the dexamethasone group ≤ 0.5 (and thus is in the range of both the Bernini and Huh study), and
- the lognormal mean of the placebo group is 4.0, 4.1, 4.2, or 4.3, and

- the lognormal mean of the dexamethasone group is 3.6, 3.7, 3.8, 3.9, or 4.0, and
- the mean difference in LOS between the two treatment groups is ≥ 30 hours.

If we wish to vary assumptions, we would see differences in the number of subjects needed.

14 HUMAN SUBJECTS PROTECTION

14.1 Discontinuation of Study

NHLBI reserves the right to discontinue the study at any time for administrative reasons. Safety will be monitored by the NHLBI-designated DSMB, which can recommend suspension or termination of the trial for safety reasons at any time. The DSMB will receive expedited reports for deaths or unexpected SAEs and regular summaries as described in Section 10. Imbalances in the numbers of SAEs and AEs between treatment groups are monitored regularly and reported to the DSMB as well. Subjects can discontinue for any reason at any time during the trial, with no consequences to the quality of their treatment. Investigators will be reimbursed for reasonable expenses incurred to the date of discontinuation on the basis of completed subjects.

14.2 Ethics

14.2.1 Good Clinical Practice and IRB Review

Compliance with GCP guidelines for the conduct and monitoring of this clinical trial will occur through observation of the ethical and regulatory requirements presented in ICH E6, *Good Clinical Practice: Consolidated Guideline*. By signing this protocol, the investigator agrees to adhere to these requirements. The study (protocol, informed consent, advertisements, Clinical Investigator Brochure, subject information sheets, Investigator CV and credentials) should be reviewed and approved by the IRB or ethics committee. Changes to the protocol will be initiated by the NHLBI and approved by the IRB. Subjects must sign written informed consent prior to being screened and before undergoing any study procedures.

The investigators and institutions affiliated with this study will permit trial-related monitoring, audits, IRB/IEC review, and regulatory inspection(s) by providing direct access to source documents.

14.2.2 Informed Consent

Informed consent is an ongoing process that includes the signing of an informed consent document. Subjects are required to sign an informed consent prior to being screened and before undergoing any study procedures or assessments, in accordance with ICH E6; 4.8, “Informed Consent of Trial Subjects.” When substantial modifications are made to the informed consent form, the DSMB or IRB may require all subjects currently enrolled in the study to be re-consented; ICH E6; 4.8 guidelines would still apply. A sample informed consent form will be provided to the sites for modification to comply with the requirements of their local IRB. The informed consent form will adhere to the guidelines in ICH E6; specifically, it will contain the elements as specified in Section 4.8.10 of that guideline. The CSCC Regulatory Specialist and NHLBI will review substantive changes suggested by the IRB to assure that all participants are adequately informed prior to participating in the study.

The site should follow the sample informed consent as closely as possible. The informed consent can be modified to include IRB required language; the template language should not be deleted. The SDMC and NHLBI will review each site’s informed consent to ensure that all of the key issues are appropriately covered in each site’s informed consent.

Subjects will be provided with a copy of the informed consent and printed materials that explain the purpose of the study, the medication(s) used in the study, procedures, and assessments. Subjects will also be provided with the telephone numbers of the investigator and qualified personnel who can assist with their questions and concerns.

